Study Procedures and Assessments	
Subjects who meet all of the inclusion criteria and none of the exclusion criteria will be assigned to either one of the monitoring groups and then followed for the duration of their hospital stay.
 
The monitoring groups will be enrolled in two prospective phases: telemetry monitoring (TM) OR surveillance monitoring. Enrollment of the TM group will occur first. After TM enrollment is complete, the enrollment phase of SM will initiate.
 
The TM group will serve as the control group and will be monitored via the site's standard of care telemetry practice/protocol. Subjects will continue to be enrolled in the study if subjects are transferred to medical-surgical unit after initial period of TM. No additional monitoring will be used for duration of study enrollment.
 
The SM group will undergo placement of the study device following study enrollment and hospital staff will implement the SM strategy for the duration of study enrollment. A dedicated medical-surgical unit(s) will be utilized for the SM phase.
 
Study procedures during the hospital stay will involve assessing eligibility, collecting baseline information, documenting clinical data from the eMR, unit transfers, discharges, and evaluating changes in health status.
 
All study related subject data will be documented and entered into the subjects' eCRF. All treatment will be standard of care per institutional practice.

Safety Assessments	Subjects will be monitored for Serious Adverse Events and Device-Related Adverse Events as noted in Section 12.
Statistics	Baseline and study outcomes will be summarized using descriptive statistics. One-way analysis of variance will be used to compare continuous variables (e.g., age, length of study) and Chi-square or Fisher's exact test will be used for categorical variables. Multivariate regression will be used to assess impacts of potential confounders. A P-value <0.05 is considered statistically significant unless otherwise specified.

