### 9.3. Inclusion Criteria

Each subject must meet the following criteria to be enrolled in the study:

1. Signed and dated informed consent by subject
2. Male or female 18 years of age or older
3. Expected hospitalized admission on the general care floor or medical surgical unit for at least one overnight stay and/or  $> 12$  hours
4. Scheduled for telemetry monitoring
5. Diagnosis indicates AHA telemetry Class III or none and therefore not indicated for telemetry monitoring
6. For SM group subjects, treating provider who scheduled subject for telemetry agrees to alternative monitoring plan of surveillance monitoring
7. Willingness to have study devices attached and hair shaved at sensor location as needed during study participation
8. Willingness to participate in all aspects of the study

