### **Surveillance Monitoring (SM) Group**

Subjects in the SM group will alternatively be admitted to a medical surgical unit and placed with the study device following study enrollment. Hospital staff will utilize SM for the duration of study enrollment.

The sponsor and investigator will collaborate to implement the SM strategy. This implementation could include a variety of strategies based on the site's facilities, staffing resources, and IT infrastructure. The Vital Sync™ IM & VPMP conveys physiologic data, waveforms, and will provide visual alerts and annunciation alarms. Alert and alarm thresholds will be customized as needed to align with the hospital's protocols. Data from the remote monitoring platform will be accessed at a central workstation, a workstation on wheels, a bedside tablet, and/or smartphones/tablets.

Subjects will be tracked daily to confirm continuing eligibility for the study. Temporary alternate monitoring modalities will be allowed per the discretion of the Investigator. If subject no longer meets eligibility criteria, the subject should be withdrawn and study completion date will be the date the subject became ineligible not the date the study team discovered the ineligibility.

If a subject is transferred to another hospital unit, subject will continue to be enrolled in the study. However, the subject will be removed from SM during the transfer including placement of BioModule. When the subject transfers back to the medical-surgical unit, SM should resume as soon as reasonably possible per discretion of the Investigator until discharge from the hospital or end of study enrollment.

If subject is transferred to ICU, there will be an exception to the requirement of tracking daily continuing eligibility. It is expected for additional care and monitoring to be administered during the ICU stay and AHA indication to change. Once subject is transferred from the ICU back to a lower acuity unit, eligibility criteria will be reassessed and documented. If subject no longer meets eligibility criteria upon return to lower acuity unit, the subject should be withdrawn from the study. If subject meets eligibility criteria daily, subject will resume SM procedures and daily tracking of eligibility criteria.

[figure not shown]
This document is electronically controlled. Printed copies are considered uncontrolled.

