#### **10.6. Randomization**

No randomization will be used during the course of the study. Assignment to a monitoring arm will be determined by the phase status of the study. During the TM phase, all subjects will be assigned to the TM group. During the SM phase, all subjects will be assigned to the SM group.

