### 13.3. Statistical Analysis

In general, descriptive statistics will be used to summarize baseline and study outcomes. For continuous variables, number of available observations, mean, standard deviation, median, minimum and maximum values will be provided. For categorical variables, frequency and percentage will be used. Unless otherwise specified, statistical assessments will be based on 2-sided tests at an alpha level of 0.05, which include Student-t or Wilcoxon rank-sum or ANOVA test for continuous variables, and Chi-square or Fisher's exact test for categorical variables. Multivariate regression models will be used to assess impacts of potential confounding variable. [REDACTED].

The primary effectiveness analysis will be based on all evaluable data from this study. A per protocol analysis will be performed based on all subjects who are compliant with the study protocol, i.e. who provide valid informed consents.

For safety assessments, adverse events (AEs) will be summarized using frequency counts and percentages. Descriptive statistics will be provided by monitoring group and by severity and relationship. Additionally, differences between the two monitoring groups will be summarized along with 95% confidence intervals. Individual listings of adverse events, including event type, start date, duration,

This document is electronically controlled. Printed copies are considered uncontrolled.

Monitoring visits will be conducted at the start, during and at the closure of the clinical study in accordance with Medtronic internal SOPs and the Monitoring Plan. An interim monitoring visit may be combined with the closing monitoring visit.

Frequency of monitoring visits will occur based on subject enrollment, duration of the study, study compliance, findings from previous monitoring visits and any suspected inconsistency in data that requires investigation. Regulatory documents (e.g., Informed Consent Form, IRB approval letters and Clinical Trial Agreements, etc.) will be reviewed at the study center.

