**Confidential**

## 7.2. General Methodology

In general, descriptive statistics will be used to summarize baseline and study outcomes. For continuous variables, number of available observations, mean, standard deviation, median, minimum and maximum values will be provided. For categorical variables, frequency and percentage will be used. Unless otherwise specified, statistical assessments will be based on 2-sided tests at an alpha level of 0.05, which include Student-t or Wilcoxon rank-sum or ANOVA test for continuous variables, and Chi-square or Fisher's exact test for categorical variables. Multivariate regression models will be used to assess impacts of potential confounding variable. Statistical analysis will be performed using [REDACTED] (SAS Institute Inc., Cary, NC) or other valid statistical software.

The primary effectiveness analysis will be based on all evaluable data from this study. A per protocol analysis will be performed based on all subjects who are compliant with the study protocol, i.e. who provide valid informed consents and do not experience any major protocol deviations.

For safety assessments, adverse events (AEs) will be summarized using frequency counts and percentages. Descriptive statistics will be provided by monitoring group and by severity and relationship. Additionally, differences between the two monitoring groups will be summarized along with 95% confidence intervals. Individual listings of adverse events, including event type, start date, duration, severity, and device-relatedness will be provided as appropriate. The safety analysis will be based on all patients participated in the study.

Further, a health economic analysis will be performed based on healthcare economic and resource utilization data collected in this study. Monitoring effectiveness, QoL in the form of Quality-Adjusted Life-Years (QALYs), life-years gained and other data collected in this study may be used as inputs to the model.

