## 7.6. Demographic and Other Baseline Characteristics

Demographics, medical history, hospital admission data and other baseline characteristics data listed in section 10.2.1 of CIP will be summarized by descriptive statistics.

This document is electronically controlled. Printed copies are considered uncontrolled.

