## 7.9. Evaluation of Objectives

The primary study endpoint is hospital of length of study (LOS), which is calculated from date of admission and discharge. The primary objective is to demonstrate that LOS of the SM group is similar (non-inferior) to the TM group.

Additionally, if the non-inferiority objective is met, superiority will also be assessed (without statistical penalty) to further understand the effectiveness of SM versus TM. The corresponding superiority hypothesis becomes: [REDACTED] (i.e., SM has shorter LOS duration than TM).

Secondary clinical and qualitative endpoints include:

- number of RRT interventions between monitoring groups
- survival rates post RRT interventions between monitoring groups
- Time of RRT activation to time of threshold notifications from SM system following clinical deterioration events
- code blue rates between monitoring groups
- unplanned intubations between monitoring groups
- clinical team satisfaction with surveillance monitoring and study product
- patient satisfaction with surveillance monitoring and study product
- perceptions of clinicians who prescribe telemetry to patients without AHA indication
- Clinicians' perceptions on telemetry utilization and impact on hospital resource utilization and patient flow

Additionally, healthcare economic and resource utilization data will be collected to evaluate:

- telemetry bed, ED, and ICU bed availability between monitoring periods
- associated health care costs between monitoring periods

This document is electronically controlled. Printed copies are considered uncontrolled.

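### Provider agreement screens entry to the surveillance phase only, and the visible plan gives confounder regression no stated role in the length-of-stay decision

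*Protocol*

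**What the plan says.** Allocation (Protocol 10.6, repeated in SAP Section 5): there is no randomization, and "Assignment to a monitoring arm will be determined by the phase status of the study". TM subjects are enrolled first, SM subjects afterwards.

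Entry (Protocol 9.3, criterion 6, also in the Synopsis): "For SM group subjects, treating provider who scheduled subject for telemetry agrees to alternative monitoring plan of surveillance monitoring". It is the only entry criterion worded for one group.

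Tests: the SAP's general list of two-sided 0.05 tests reads "which include Student-t or Wilcoxon rank-sum or ANOVA test for continuous variables" (SAP 7.2; same in Protocol 13.3). The Synopsis names only one-way analysis of variance for continuous variables.

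Adjustment: the Synopsis says "Multivariate regression will be used to assess impacts of potential confounders", and Protocol 13.3 and SAP 7.2 say "Multivariate regression models will be used to assess impacts of potential confounding variable". No outcome, covariates, scale or model form is visible.

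Decision: SAP 7.9 states "The primary objective is to demonstrate that LOS of the SM group is similar (non-inferior) to the TM group", then a superiority test if that succeeds. It does not mention regression. On baseline data, SAP 7.6 says only "Demographics, medical history, hospital admission data and other baseline characteristics data listed in section 10.2.1 of CIP will be summarized by descriptive statistics".

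Parts of Protocol 13.2 and SAP 7.9 around the hypotheses are redacted, as is the text just after the regression sentence in Protocol 13.3. This point therefore concerns the visible text.

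**The concern.** A patient whose provider wants to keep telemetry can enter the TM group but not the SM group. If providers tend to refuse SM for patients whose expected stay differs from the rest, an unadjusted SM/TM ratio mixes that selection with the effect of monitoring. If refused patients stay longer, false non-inferiority and false superiority become more likely. If they stay shorter, power falls.

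In a non-randomized comparison the adjustment model is part of the primary inference. Here the model, the covariates and their role are open. An adjusted result that disagrees with the unadjusted test would have no defined standing, and covariates could be chosen after LOS has been seen.

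**Working it through.** **Inputs.** From Protocol 13.1 and SAP Section 6: coefficient of variation (CV) 0.65, margin 0.2 on the mean ratio (read as an upper limit of 1.2 for SM/TM), similar LOS distributions, 132 per group, more than 80% power, significance level 0.05. Sidedness is not stated there, so both one-sided 0.05 and 0.025 are shown. Lognormal LOS is assumed.

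**The plan's own figure.**
- SD of log LOS = √ln(1 + 0.65²) = 0.5936; ln 1.2 = 0.1823.
- n per group = 2 × (1.645 + 0.842)² × 0.5936² / 0.1823² ≈ 131.1, rounded up to 132. This reproduces the plan at one-sided 0.05, as a two-group comparison with no covariate term. One-sided 0.025 would give 167.
- Standard error (SE) at 132 per group = 0.5936 × √(2/132) = 0.0731.
- Power at a true ratio of 1 = Φ(0.1823/0.0731 − z) = 80.2% (z = 1.645) or 70.4% (z = 1.960).

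**How large a shift matters.** Let selection lower the observed log ratio by b. Then false non-inferiority at a true ratio of 1.2 = Φ(b/SE − z).
- 5% to 10%: b = (1.645 − 1.282) × 0.0731 = 0.0266, a factor of 1.027.
- 2.5% to 5%: b = (1.960 − 1.645) × 0.0731 = 0.0230, a factor of 1.023.

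False superiority at a true ratio of 1 has the same form. The visible rule is two-sided 0.05, so only z = 1.960 applies: a 2.3% shift takes it from 2.5% to 5%.

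**What refusal would have to look like.** This is pure assumption. If a share f of eligible patients would be refused and their LOS is k times the rest, then b = f × ln k.

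| f, k (assumed) | b | Quantity | One-sided 0.05 | One-sided 0.025 |
|---|---|---|---|---|
| 0.1, 1.25 | 0.0223 | False non-inferiority | 9.0% | 4.9% |
| 0.2, 1.5 | 0.0811 | False non-inferiority | 29.6% | 19.8% |
| 0.3, 1.5 | 0.1216 | False non-inferiority | 50.8% | 38.4% |
| 0.1, 0.80 | −0.0223 | Power at ratio 1 | 70.7% | 59.1% |
| 0.3, 0.667 | −0.1216 | Power at ratio 1 | 20.8% | 12.9% |

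Power uses Φ((0.1823 + b)/SE − z). The spread of the table reflects the chosen f and k and nothing in the documents.

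**The case against.** The strongest reply is that confounder adjustment is already planned in three places and baseline data are scheduled, so detail is missing rather than control. That is right as far as it goes. A reader might infer that no adjustment is planned, and the documents contradict that. What stands is that nothing visible says which model is used or whether it can change the decision.

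Second, redaction. The hidden text in Protocol 13.2 and SAP 7.9 could hold more than hypotheses. The gap in Protocol 13.3 sits where SAP 7.2 has its software statement, so it is probably that, but this is an inference. The list of tests is also open-ended. The point therefore has to stay with the visible text.

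Third, no evidence of bias. No refusal rate, and no link between refusal and LOS, is given, and the population is already limited to patients without an AHA indication. This stands. The doubling figures show how sensitive the comparison is, not that the criterion causes a shift.

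Fourth, a reader might infer that refusals before consent go unrecorded. Protocol 10.3 does not support that: the log covers pre-screened as well as screened patients and records reasons for ineligibility. At most the wording needs clarifying.

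Fifth, age, sex and diagnosis may not capture a provider's judgment, and a pre-specified adjusted sensitivity analysis would also give a conflicting result a defined standing. Both are fair. Letting the adjusted ratio decide is preferred because the groups are not randomized and one of them is filtered by rule.

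**Conclusion.** The point holds for the visible text: entry is filtered in one group only, allocation is by phase, the named tests are unadjusted, and the planned regression has no stated part in the LOS decision. It should be changed. That this is a single-center pilot limits its weight but does not remove it, because the study has a powered non-inferiority objective.

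The size is illustrative. At 132 per group and CV 0.65, with lognormal LOS and a margin of 1.2, a selection shift of 2.7% (one-sided 0.05) or 2.3% (one-sided 0.025) doubles false non-inferiority. For superiority only the 2.3% figure applies.

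Two stronger readings are not supported. One is that the comparison is biased in favor of SM: the documents give no direction, and a shift the other way would cost power instead. The other is that error rates near 50% are to be expected: that needs 30% refusals with stays 1.5 times as long, both assumed.

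**What to change.** 1. In SAP 7.9, state that the SM/TM ratio deciding both non-inferiority and superiority comes from a linear model for log LOS with monitoring group, age, sex and primary-diagnosis group, plus any medical-history items named from the eCRF. Fix the diagnosis groups and history items before LOS data are analysed. If no history items are named by then, use the first four terms. Exclude the admitting unit and any other variable determined by group, because by design "Subjects in the SM group will alternatively be admitted to a medical surgical unit" (Protocol 10.1). Keep the unadjusted test as a sensitivity analysis.
2. Report the number of SM-phase provider refusals from the existing Screening and Enrollment Log (Protocol 10.3), clarifying its wording if needed.
3. State as a limitation that adjustment removes only measured case-mix differences and cannot remove calendar effects.

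Cost: some SAP wording and one added model. Demographics (taken to include age and sex), medical history and primary diagnosis are already in Protocol Table 1. The documents do not itemise the history fields, hence the reference to the eCRF. Residual confounding remains, and how much of any shift the covariates capture is unknown. The model gives a ratio of geometric means, which equals the mean ratio only under the common CV assumed in Protocol 13.1 and SAP Section 6.

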### 9.4. Exclusion Criteria

Subjects who meet any of the following criteria will be excluded from the study:

1. Implanted pacemaker or automatic defibrillator
2. Allergy or sensitivity to ECG leads or adhesives that are similar to ECG leads
3. Current AHA Class I or II indication/prescription for telemetry monitoring
4. Prescription for other continuous condition monitoring such as capnography or pulse oximetry
5. Ongoing opioid therapy by PCA, by epidural or intrathecal infusions or by intravenous analgesia, per Investigator discretion
6. Ventilated or intubated patients at the time of enrollment
7. Female subject is pregnant, lactating, trying to get pregnant, or has a positive pregnancy test for women with childbearing potential (**see Section 9.5**)

This document is electronically controlled. Printed copies are considered uncontrolled.

8. Condition that, in the opinion of the investigator, may prevent completion of the study or protocol requirements
9. Subject is considered as being morbidly obese (defined as BMI >50.0)

## 9.5. Childbearing Potential and Pregnancy Testing

Pregnancy testing will only be performed in women with childbearing potential. Women of nonchildbearing potential are defined of self report of any female who meets one of the following condition.

- Postmenopausal defined as amenorrhea for at least 2 years.
- Surgically sterile (have had a hysterectomy or bilateral oophorectomy, tubal ligation, or otherwise be incapable of pregnancy)
- Abstinent (at the discretion of the investigator)
- Having other congenital or medical condition that prevents subject from becoming pregnant

Women of childbearing potential must have a negative serum  $\beta$ -human chorionic gonadotropin ( $\beta$ -hCG) pregnancy test or a negative urine pregnancy test prior to placement of any monitoring devices.

## 10. Study Procedures

Each enrolled subject will be assigned to one of two types of monitoring arms: telemetry monitoring (TM) OR surveillance monitoring (SM) and then followed for the duration of their hospital stay up to 30 days ( $\pm$  2 days). The monitoring groups described in Section 10.1 will be enrolled in two prospective phases. The enrollment phase of the TM group will occur first. After TM subjects have completed study participation, the SM phase will initiate.

The SM phase will begin with a tuning period to educate the hospital staff so they can obtain experience using the SM system within their workflow. No subjects will be enrolled in the study during this time as hospital staff will be able to pilot the SM system within hospitalized patients.

Study flowchart is reported in Figure 1.

### 10.1. Monitoring Group Assignment

#### Telemetry Monitoring (TM) Group, Control

The TM group will serve as the control group and will be monitored via the site's standard of care telemetry practice/protocol. Subjects will continue to be enrolled in the study if subjects are transferred to medical-surgical unit after initial period of TM. Subjects will be tracked daily to confirm continuing eligibility for the study. Temporary alternate monitoring modalities will be allowed per the discretion of the Investigator. If subject no longer meets eligibility criteria, the subject should be withdrawn and study completion date will be the date the subject became ineligible not the date the study team discovered the ineligibility.

If a subject is transferred to another hospital unit or telemetry is discontinued, subject will continue to be enrolled in the study.

If subject is transferred to ICU, there will be an exception to the requirement of tracking daily continuing eligibility. It is expected for additional care and monitoring to be administered during the ICU stay and AHA indication to change. Once subject is transferred from the ICU back to a lower acuity unit, eligibility criteria will be reassessed and documented. If subject no longer meets eligibility criteria upon return to

This document is electronically controlled. Printed copies are considered uncontrolled.

